Aim 1: Work outcomes. The primary analysis is intention-to-treat and the primary outcome is total weeks worked in competitive jobs with primary endpoints of 6 and 9 months. Power estimate for total weeks worked was calculated using simulated data from a three-level linear regression model to account for the nested structure of the data. Simulation studies are the most flexible method for power analysis which can be tailored to any kinds of analyses. SAS 9.4 was used to generate 1000 datasets from each hypothesized model with plausible effect sizes for parameters of interest based on pilot data. Power estimates are based on the percentage of the datasets (replications) in which the parameters were significant. Based on the open trial pilot data, an ICC of .077 was estimated for the clustering effect of cohort and an ICC of .2 for repeated measures. Our pilot data show that CBTw significantly increased total weeks worked at 6 months ($f^2 = .15$). It is anticipated that there will be a larger increase in total weeks worked over time for the treatment arm. With the target sample size, there will be 97.6% power to detect even a small study arm by time interaction effect ($f^2 = .03$) with type I error set at .05. Further, the outcome distribution is likely to be non-normal. Although power will be attenuated by this non-normality, power to detect the target effects is still expected to be sufficient (>80%). For the binary outcome of achievement of steady competitive work, CBTw pilot data show that 49% of participants who were unemployed at baseline became steady workers at 6 months. In WORKWELL, it is expected that 5-10% more participants will acquire work and become steady workers during by the 9 month follow-up. Thus, power estimates may be conservative. In the control arm, it is anticipated that approximately 34% will become competitively employed and a lesser number will be steady workers by 9 months, based on VHA program evaluation data reporting 1-year SE outcomes. Based on the effect size, simulated data was used from two level logistic regression models, finding that the target sample size will provide > 99% power to detect the treatment effect, accounting for a conservative estimate of 13% attrition. If more participants gain competitive employed in the control arm (~50%), there will be >80% power to detect this effect.

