Aim 2: Health and recovery outcomes. Two-level linear regression models accounting for the nested nature of the data (repeated measures nested within individuals) will be used to examine the effects of CBTw + SE services compared to psychoeducation + SE on the change of each of the continuous outcomes including recovery (RAS), health-related quality of life (PCS & MCS), symptoms (DSM), and suicidality (SSI) over time (baseline and 3-, 6-, 9-months follow-ups). It is expected that there will be adequate power (>80%) to detect the treatment effect on health and recovery outcomes even if the effect size is small (i.e., $f^2 = .03$). *Regarding the outcome of suicidal ideation, it is anticipated that the range of responses will be smaller, given that fewer participants will report these thoughts (21.2% of participants in the CBTw open pilot reported passive ideation at baseline; 9.6% reported such thoughts at follow up). Thus, the study may be less powered to detect a treatment effect. However, despite this issue of range restriction given the relatively lower base rate of suicidal thoughts, WORKWELL will nonetheless examine possible treatment effects, due to the importance of this outcome in Veterans with SMI.*

Preliminary analysis: Baseline characteristics of sample & covariates analyses

Given the RCT design, characteristics of participants are expected to be balanced across the two study arms. Baseline characteristics and baseline clinical outcomes (e.g., symptoms) will be compared between the arms using the appropriate test (i.e., t-test, or Chi-square test). Variables found to significantly differ will be included as covariates in the primary analyses. All primary analyses will also include time receiving SE services and site membership as covariates. The potential interaction effects of site with key predictors will also be included as predictors to account for the site effect. Lastly, attendance (the number of CBTw or psychoeducation sessions attended) and the association with the Aim 1 and Aim 2 outcomes will be examined.

Aim 1 Analyses: Competitive Work Outcomes

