Hypothesis 1: For the outcome, total weeks worked in competitive jobs, three-level linear regression models will be used to test the effects of CBTw + SE compared to psychoeducation + SE over time, with predictors of study arm, arm by time interaction, site, and interaction between site and key predictors, covariates, as well as random effects to accommodate the potential non-independence due to repeated measures and group cohort effects. The time effects could be linear or nonlinear; these possibilities will be examined by treating time as continuous or categorical. If the outcomes are not normally distributed, robust maximum likelihood estimation method will be used to correct the standard error estimates for nonnormality. In the case of excess of zeros for this outcome, hurdle negative binomial models, a reliable method to analyze zero inflated longitudinal data of this nature, will be utilized. For the binary outcome, steady competitive work status across the 9-month study period, two-level logistic regression model will be used with the same set of predictors as in the linear models, with random effects to accommodate the potential non-independence due to group cohort effects.

Aim 2 Analyses: Health and Recovery Outcomes

To test **Hypothesis 2a**, Two-level linear regression models accounting for the nested nature of the data (repeated measures nested within individuals) will be used to examine the effects of CBTw + SE services compared to psychoeducation + SE on the change of each of the continuous outcomes including recovery (RAS), health-related quality of life (PCS & MCS), symptoms (DSM), and suicidality (SSI) over time (baseline and 3-, 6-, 9-months follow-ups). The scores of the outcome measures are calculated by averaging the corresponding items. The models are the same as those in Aim 1 analysis except that the outcomes are different. It is hypothesized that CBTw + SE will lead to a greater improvement on the health and recovery outcomes (indicated by a significant arm by time effect). If the outcomes are not normally distributed, robust maximum likelihood estimation method will be used to correct the standard error estimates for nonnormality.

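### The SAP lists no covariate-by-time terms (site aside), so in its linear models the baseline-imbalance adjustment cannot correct the arm-by-time test that decides Hypothesis 2a and was powered for Aim 1

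*SAP*

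**What the plan says.** - **Imbalance rule** (SAP, Preliminary analysis): "Variables found to significantly differ will be included as covariates in the primary analyses". The functional form is not given.
- **Fixed covariates** (same section): "All primary analyses will also include time receiving SE services and site membership as covariates".
- **Site only is crossed** (same section): "The potential interaction effects of site with key predictors will also be included as predictors to account for the site effect".
- **Aim 1 model** (SAP, Aim 1 Analyses, Hypothesis 1): three-level linear regression "with predictors of study arm, arm by time interaction, site, and interaction between site and key predictors, covariates, as well as random effects". The Hypothesis 1 paragraph in the Protocol's Data Analysis section lists the same terms.
- **Aim 2 model** (SAP, Aim 2 Analyses, Hypothesis 2a): "The models are the same as those in Aim 1 analysis except that the outcomes are different". The response runs "over time (baseline and 3-, 6-, 9-months follow-ups", and the hypothesis is supported by greater improvement, "indicated by a significant arm by time effect". The Protocol's Hypothesis 2a paragraph specifies no covariate terms.
- **Aim 1 power** (SAP, Sample size and power): "97.6% power to detect even a small study arm by time interaction effect".
- **Hypothesis 1** (Protocol 3.2) is worded as more weeks worked and a greater chance of steady work. The SAP sets endpoints at 6 and 9 months.

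**The concern.** The imbalance rule implies that a chance difference between arms will be dealt with in the primary analyses. But a covariate fixed at baseline and entered without a time interaction only moves a Veteran's whole profile up or down. A test of arm by time compares changes, and a constant shift cancels out of a change.

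If the imbalanced variable predicts how fast the outcome changes, its contribution to the arm difference in slopes stays in the estimate, and no precision is gained. The Protocol (Other measures and covariates) itself cites an association between work history and later work outcomes, so prognostic baseline variables are expected here. The analyst would report an adjusted result that, for the tested term, equals the unadjusted one.

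**Working it through.** **The plan's own figure.** The 97.6% power cannot be reproduced with certainty, because the simulation settings are not given. A noncentral F approximation (1 df, f² = .03, alpha .05 taken as two-sided) runs from 57.5% to over 99.9%, depending on the number of visits and how the ICCs (.077 cohort, .2 repeated measures) are applied. One variant comes close: 276 × 0.87 ≈ 240 Veterans, × 3 visits ÷ [1 + 2 × .2 = 1.4] ≈ 514 effective observations, giving 97.5%. The figure is neither confirmed nor refuted. What matters here is which term it refers to: arm by time.

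**Why a main effect drops out.** With complete data at common visits, arm by time is the difference between arms in mean personal slope, where

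b_i = Σ(t − t̄)y_it / Σ(t − t̄)².

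Adding γx_i to every visit of Veteran i adds γx_i Σ(t − t̄) / Σ(t − t̄)² = 0. If the covariate also changes the slope by δ per unit, b_i gains δx_i, and the arm contrast shifts by δ(x̄₁ − x̄₀). Only a covariate-by-time term can remove that shift.

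**Numerical check.** From the documents: 276 Veterans, 1:1 allocation, both ICCs, 13% attrition. Assumed, because the documents give no values: imbalance 0.3 SD, covariate effect 0.5 on level and 0.15 on slope, true arm by time 0.30. Expected shift: 0.15 × 0.3 = 0.045.

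| Arm by time | No covariate | Main effect | Plus covariate × time |
|---|---|---|---|
| Complete data, linear time | 0.3346 (SE 0.0474) | 0.3346 (SE 0.0474) | 0.2912 |
| Complete data, categorical time, month 9 | 1.0210 | 1.0210 | 0.8832 |
| 13% covariate-dependent dropout, mean of 12 datasets | 0.347 | 0.350 | 0.306 |

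The first two rows are one simulated dataset, so their last column need not equal the truth. With dropout, adding the main effect changed the estimate by 0.003-0.005 on average, against a sampling SD of about 0.04.

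These fits used a person random intercept. A separate generalised least squares fit with person intercept, person slope and cohort intercept gave 0.36412 (SE 0.06346) with and without the main effect. With 13% dropout it gave 0.274 against 0.277.

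**Size of the consequence.** Let r be the correlation between the covariate and a Veteran's slope, and suppose the imbalance sits at z = 1.96, just enough to trigger the rule. Under no treatment effect the arm-by-time z is then N(1.96r, 1 − r²), so conditional error = P(|N(1.96r, 1 − r²)| > 1.96). Crossing the covariate with time multiplies the standard error by √(1 − r²), so a test with 80% power moves to Φ[(1.96 + 0.84)/√(1 − r²) − 1.96].

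| r (assumed) | Shift, in SE (1.96r) | Conditional error | 80% power becomes |
|---|---|---|---|
| .2 | 0.39 | 6.3% | 82% |
| .3 | 0.59 | 7.9% | 84% |
| .45 | 0.88 | 11.4% | 88% |

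**Where a main effect does work.** In the same kind of simulated data:
- The 6-month arm difference moved from 0.840 (SE 0.127) to 0.609 (SE 0.085). A covariate-by-time term gave the same 0.609, since month 6 is the midpoint of the three follow-ups.
- The steady-work log odds ratio moved from 0.734 to 0.625 (truth 0.60).
- With non-linear links arm by time does respond: logit 0.172 to 0.185; negative binomial, mean absolute change 0.03. These were marginal models, not the full hurdle model.

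**The case against.** **The covariate form is inferred.** No sentence says main effects only, and the list of terms is shorthand: it omits even the main effect of time. That is fair. But the list spells out interactions for site and none for the other covariates, so main effects is the natural reading. If another form was meant, the SAP needs to say so.

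**A reader might infer that the adjustment does nothing for either hypothesis.** The documents do not support this. Hypothesis 1 is worded as more weeks worked and more steady workers, the model contains an arm term, and steady work has its own logistic model. Main-effect covariates adjust all of these, as shown above. The SAP powers arm by time for Aim 1 but does not name it as the deciding test. Nor does a constant covariate effect spoil the 6-month contrast.

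**The identity has limits.** It is exact only for linear models, complete data and covariates constant over time. The SAP switches to a hurdle negative binomial model if weeks worked has excess zeros, and the identity does not extend to that. The Protocol defines time in SE as days receiving services without restricting it to before baseline. If it accrues during follow-up, it is not constant.

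**The harm is modest.** Under randomisation the unadjusted arm-by-time test keeps its nominal error across all trials. The 6-11% applies only given the imbalance, and the correlations are assumptions. Part of the gain is efficiency, and with categorical time the parameter cost is larger. All of this stands and limits the size of the point. It does not restore the adjustment for Hypothesis 2a.

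**Conclusion.** The point holds for the linear mixed models. Entered as listed, covariates fixed at baseline leave arm by time unchanged with complete data and almost unchanged at 13% dropout. The adjustment promised for baseline differences is therefore ineffective for Hypothesis 2a, where arm by time is the stated criterion, and for any Aim 1 test of that term.

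It does not hold for visit-specific differences in weeks worked, for the steady-work model or for the hurdle fallback. It should not be read as a claim of inflated overall error. The conditional error of about 6-8% and the power gain from 80% to about 82-84% rest on an assumed r of .2-.3; r = .45 gives 11% and 88%. The identity itself rests on algebra and does not depend on r or on which covariates are chosen.

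This should be changed before analysis. It is more than missing detail, because following the listed model leaves a promised correction without effect on a deciding test.

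**What to change.** In the SAP's Aim 1 and Aim 2 Analyses and the matching Protocol Data Analysis paragraphs:

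1. For Hypothesis 2a and any Aim 1 arm-by-time test, enter each baseline covariate together with its interaction with time, coding time as in the arm-by-time term. Alternatively, test a visit-specific, covariate-adjusted contrast.
2. Fix time in SE services at its baseline value.
3. Name the contrast that decides Hypothesis 1 for weeks worked.

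The cost is a few sentences and one extra parameter per covariate with linear time, or several with categorical time. No new data are needed.

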## **5.5 Inclusion/Exclusion Criteria**

### **5.5.1 Veterans**

#### ***Inclusion criteria***

1) Unemployment, defined as no current participation in a competitive job; 2) a competitive work goal; 3) Presence of a serious mental illness (required to receive SE services); 4) Receiving SE services; 5) Age 18 or older.

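### If zeros are excessive, the primary analysis switches to a hurdle model with no named contrast, and neither of its two arm effects is the intention-to-treat effect on total weeks

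*SAP*

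**What the plan says.** SAP, Sample size and power, Aim 1: "The primary analysis is intention-to-treat and the primary outcome is total weeks worked in competitive jobs with primary endpoints of 6 and 9 months". Protocol section 3.2 states Hypothesis 1 in terms of weeks worked.

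SAP, Aim 1 Analyses, gives the default model: "three-level linear regression models will be used to test the effects of CBTw + SE compared to psychoeducation + SE over time". It includes arm and arm-by-time terms, random effects for repeated measures and group cohort, and robust maximum likelihood if the outcome is not normal. The fallback follows: "In the case of excess of zeros for this outcome, hurdle negative binomial models, a reliable method to analyze zero inflated longitudinal data". The Protocol's data analysis section (Hypothesis 1) has the same sentence.

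Two further statements bear on how many zeros to expect. Protocol section 5.5.1 makes this an entry criterion: "Unemployment, defined as no current participation in a competitive job". For controls, the SAP says "it is anticipated that approximately 34% will become competitively employed and a lesser number will be steady workers by 9 months", and it also considers an alternative of about 50% employed.

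Neither document says what counts as an excess of zeros, which hurdle coefficient tests Hypothesis 1, whether the two parts are tested jointly, or whether they are recombined into a mean over all randomised Veterans. The missing-data sensitivity analyses do not cover this.

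**The concern.** A hurdle negative binomial model has two parts. One is a binary model for zero against any weeks, fitted to everyone. The other is a zero-truncated count model, fitted only to those with at least one week. Each has its own arm effect, and with arm-by-time terms there are more candidate coefficients still.

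The zero part is a randomised comparison, but of a different outcome: finding any job. The count part concerns weeks, but among people selected by an event after randomisation that CBTw is meant to change. Read as they stand, the coefficients do not answer whether CBTw Veterans work more weeks. The trial could then report a primary result on a different question, choose between two results after seeing them, or report a negative count coefficient when total weeks have risen.

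**Working it through.** **1. Is the fallback likely to be used?** Everyone enters without a competitive job. With 34% of controls finding one, 1 − 0.34 = 66% have zero weeks; with about 50%, half do. For CBTw, the SAP cites a pilot share of 49% steady workers at 6 months and expects 5–10 points more by 9 months (54–59%). Steady workers are a subset of all workers, so these are minimum shares for any work. The switch is likely, though not certain.

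**2. Who enters the count part?** After 13% attrition, 276 × 0.87 ≈ 240, or 120 per arm.
- Controls: 0.34 × 120 ≈ 41.
- CBTw: 0.49 × 120 ≈ 59, rising to 0.59 × 120 ≈ 71.

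**3. What does the stated 97.6% power cover?** The SAP derives it from simulated three-level linear models (f² = .03 for arm by time, α = .05). It does not give the time points, cohort count or variance scale, so the figure cannot be rebuilt uniquely. An approximation is Φ(√(f² × n_eff) − 1.96), two-sided.
- 240 Veterans, 3 visits, repeated-measures ICC .2: n_eff = 240.1 × 3 / (1 + 2 × .2) = 514.5, power 97.55%.
- Cohort ICC .077 with 8 per group instead: design effect 1 + 7 × .077 = 1.539, n_eff = 468.1, power 96.3%.
- Both design effects multiplied: n_eff = 334.3, power 88.6%.

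The figure is plausible for the linear model. No power is stated for either hurdle part.

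**4. How do the parts relate to total weeks?** Mean total weeks = P(work) × E[weeks | work]. An illustration with assumed weeks: 34% of each arm work 14 weeks, and CBTw adds 15% who work 8.
- Control: 0.34 × 14 = 4.76 weeks overall, 14 per worker.
- CBTw: 4.76 + 0.15 × 8 = 5.96 overall; 5.96 / 0.49 = 12.16 per worker.
- Total weeks rise by 1.20; weeks per worker fall by 1.84, although nobody works less.

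**5. How often would the count part be significant against CBTw?** Simulations used 120 per arm with no clustering or repeated measures. All weeks per worker are assumed, because the documents give none. In the 54% and 59% rows, weeks were negative binomial (mean parameter 12, k = 3, restricted to 1–26); the added workers' mean parameter is shown.

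| Share working, control to CBTw | Added workers | Total weeks | Weeks per worker | Significant against CBTw |
|---|---|---|---|---|
| 34% to 54% | 8 | +1.6 | −1.1 | 12% |
| 34% to 54% | 5 | +1.05 | −2.1 | 38% |
| 34% to 59% | 5 | +1.3 | −2.4 | 49% |
| 34% to 49% (step 4) | 8 weeks | +1.2 | −1.8 | 26% |
| 34% to 49% (step 4) | 5 weeks | +0.75 | −2.7 | 49% |

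Another assumed spread gave 16% and 36% for the last two rows.

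Scenarios closer to the SAP's expectation had 49% steady in CBTw plus 5–10% non-steady, and 34% of controls working, of whom 17–30 points were steady. Steady workers had 13–26 weeks and the others 1–12. The per-worker difference ran from +5.3 to −0.7 weeks. Wrong-way significance was at most 1.2% in five of six scenarios and 7.8% in the sixth.

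If the share working rises from 34% to 54% with weeks per worker unchanged, total weeks rise by 2.15. The count part then rejects in 4.9% of runs, its null rate.

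**6. What if either part could be claimed?** With independent tests, 1 − 0.95² = 9.75%. Simulated hurdle-type tests under no effect gave 8.0–8.3%. A joint 2-df test gave 3.7–4.6%; it controls the error but does not estimate weeks.

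**The case against.** A hurdle model is fitted to all randomised Veterans, and its two parts together imply a mean over everyone. The SAP declares intention to treat and does not say that the count coefficient will be the test. This stands: a reader might infer that the fallback in itself abandons intention to treat, and the documents do not support that. The defect is the unnamed contrast.

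A reader might also infer that the plan's type I error is near 10%. It is not shown to be; the SAP has no rule that either part may count, so 8–10% describes what the wording leaves open.

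The high wrong-way rates should not be read as forecasts. The step 4 illustration makes 49% the share with any work, whereas the SAP gives 49% as the steady share. Where CBTw workers are mostly steady, reversal is rare. The sign and frequency depend on assumed weeks; the conditioning on having found work does not.

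Finally, the switch is conditional, and the SAP already provides robust estimation for a non-normal outcome. That is fair, but the sentence on zeros still replaces the linear model under conditions that the SAP's own rates make likely.

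**Conclusion.** The point holds as a gap in the primary analysis. If zeros are judged excessive, both documents move to a model whose arm coefficients test any work, or weeks among those who worked, and neither says how to get from these to the intention-to-treat effect on total weeks. With 50–66% of controls expected at zero, this is the likely route. The count part would use about 41 of 120 controls and 59 or more of 120 CBTw Veterans, with no stated power.

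The structural argument needs no simulation. The sizes do: type I error of about 8–10% only if either part may be claimed, and count-part results against CBTw in about 12–49% of runs when added workers hold short jobs, but near 0–8% when CBTw workers are mostly steady, as the SAP expects. All ignore clustering and repeated measures. Nothing here shows the 97.6% to be wrong for the linear model, or hurdle models to be unsuitable.

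**What to change.** State in the SAP and Protocol that the primary test of Hypothesis 1 is the arm difference in mean total weeks over all randomised Veterans, zeros included, at the plan's primary endpoint or endpoints. Then choose one route in advance:

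- Keep the three-level linear model with robust standard errors as primary, whatever the share of zeros. Its arm contrast at the endpoint remains a difference in mean weeks.
- If the hurdle model is fitted, compute P(work) × E[weeks | work] from both parts under each arm, average over all randomised Veterans, and test the difference with a bootstrap that resamples whole cohorts.

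In either case, report the two hurdle parts as supportive only. The Protocol names 6 months as the primary endpoint and the SAP names 6 and 9; that is a separate matter, which this change need not settle.

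The cost is a few sentences and, for the second route, a short program. The real downside is power. In the illustrative case where the share working rises from 34% to 54% with weeks per worker unchanged, the all-randomised contrast had about 70% power against 88% for the zero part. It fell to 49% and 25% when the added workers had mean parameters of 8 and 5. Power for the chosen contrast should therefore be simulated with the planned cohort and repeated-measures structure and a realistic share of zeros.
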